FFA	Fundus fluorescein angiography
FSH	Follicle-stimulating hormone
HA	Health Authority
IEC	Independent Ethics Committee
logMAR	Logarithm of the minimum angle of resolution
MedDRA	Medical dictionary for regulatory activities
OCT	Ocular coherence tomography
RPE	Retinal pigment epithelium
SAE	Serious Adverse Event
SBP	Systolic blood pressure
SD	Standard deviation
SOP	Standard Operating Procedure
VA	Visual acuity
VEGF	Vascular endothelial growth factor
VFQ-25	Visual Function Questionnaire
WOCBP	Women of childbearing potential

Glossary of terms

Assessment	A procedure used to generate data required by the study
Enrollment	Point/time of patient entry into the study; the point at which informed consent must be obtained (i.e. prior to starting any of the procedures described in the protocol)
Investigational drug	The drug whose properties are being tested in the study; this definition is consistent with US CFR 21 Section 312.3 and is synonymous with “investigational new drug” or “investigational medicinal product.”
Investigational treatment	All investigational drug(s) whose properties are being tested in the study as well as their associated treatment controls. This includes any placebos, any active controls, as well as approved drugs used outside of their indication/approved dosage or tested in a fixed combination. Investigational treatment generally does not include other treatments administered as concomitant background therapy required or allowed by the protocol when used within approved indication/dosage
Medication number	A unique identifier on the label of each investigational/study drug package in studies that dispense medication using an IRT system
Subject Number	A number assigned to each patient who enrolls into the study
Premature patient withdrawal	Point/time when the patient exits from the study prior to the planned completion of all investigational/study treatment administration and all assessments (including follow-up)
Randomization number	A unique identifier assigned to each randomized patient, corresponding to a specific treatment arm assignment
Stop study participation	Point/time at which the patient came in for a final evaluation visit or when study/investigational treatment was discontinued whichever is later
Study drug/ treatment	Any single drug or combination of drugs administered to the patient as part of the required study procedures; includes investigational drug (s), active drug run-ins or background therapy
Study/investigational treatment discontinuation	Point/time when patient permanently stops taking study/investigational treatment for any reason; may or may not also be the point/time of premature patient withdrawal
Variable	Information used in the data analysis; derived directly or indirectly from data collected using specified assessments at specified time points

Protocol synopsis

Protocol number	CRFB002DTR01
Title	A randomized, open-label non-inferiority study to compare safety and efficacy of labeled versus wait and extend regimen of Lucentis (ranibizumab) in Turkish patients with visual impairment due to diabetic macular edema.
Brief title	Study of efficacy and safety of Ranibizumab in Turkish patients with visual impairment due to diabetic macular edema.
Sponsor and Clinical Phase	Novartis / Phase III
Investigation type	Drug Research
Study type	Interventional Study
Purpose and rationale	
The purpose of this study is to demonstrate the non-inferiority of “wait and extend” regimen of ranibizumab to labeled posology in Turkish patients with visual impairment due to diabetic macular edema with respect to the mean change in BCVA at 12th month from baseline..
 
Data from RESOLVE and RESTORE trials supporting monthly assessments and PRN Lucentis injections assumed to be considered as “gold standard” for future treatment of patients with visual impairment due to diabetes macula edema as it is for wet AMD. However, there is a need to explore a more clinical feasible treatment regime to provide satisfactory treatment effect with a lower number of visits and injections. A “wait and extend” regimen has been demonstrated efficient for treatment of wAMD in SALUTE study as mentioned above and found to be safe and tolerable. The rationale of this pilot study is to show that similar approach is applicable in treatment of DME.

Primary Objective(s) and Key Secondary Objective	The primary objective of this study is to demonstrate the non-inferiority of “wait and extend” regimen of ranibizumab to labeled posology in Turkish patients with visual impairment due to diabetic macular edema with respect to the mean change in BCVA at 12 th month from baseline..
Secondary Objectives	
• to compare mean change in CRT at 12th month from baseline between two groups with OCT• to assess the number of injections needed over a 12-month treatment period with a “wait and extend” dosing regimen• to assess the number of visits needed over a 12-month treatment period with a “wait and extend” dosing regimen• to evaluate the number of patients with improvement in BCVA from baseline• to evaluate the number of patients with improvement of 5 or more letters from baseline

	
• to evaluate the number of patients with improvement of 10 or more letters from baseline• to evaluate the number of patients with improvement of 15 or more letters from baseline• to evaluate the safety of intravitreal injections of Lucentis (ranibizumab) in patients with DME• to describe the change in Patient reported functional ability of Lucentis-treated patients.
Study design	
This is a randomized controlled, multicenter, 12 month study of Lucentis (ranibizumab) that the consenting patients will participate in a screening period and will be evaluated for their eligibility to enroll the study. After the screening period and the eligibility assessment of the patient, only one eye will be selected / treated as the study eye. After eligibility confirmation at baseline, patients will be randomized into one of the treatment arms as below:
 
• Arm 1 - Labeled regime arm: Treatment will be given monthly and will be continued until maximum visual acuity is achieved (the patient's visual acuity is stable for three consecutive monthly assessments performed while on ranibizumab treatment). Thereafter patients should be monitored monthly for visual acuity. 
Treatment will be resumed when monitoring indicates loss of visual acuity due to DME. Monthly injections should then be administered until stable visual acuity is reached again for three consecutive monthly assessments (implying a minimum of two injections). The interval between two doses should not be shorter than 1 month.
 
• Arm 2 - Wait and Extend regime arm: Lucentis (ranibizumab) 0.5 mg will be injected subsequently at baseline, month 1 and 2. After the three initial loading doses, patients will be called for the control visits 1 month later. If the visual acuity has reached a stable level and there is no sign of edema on OCT, patients will not receive intravitreal injection and will be called to come back 6 weeks later. The interval is increased by 2 weeks until a maximum of 8 weeks as long as the patient presents as stable regarding visual acuity, central retinal thickness and clinical findings. If there is a negative change, the interval is shortened back to 4 weeks.
Population	The study population will consist of male and female patients (over 18 years old) admitted to hospital with Type 1 or Type 2 diabetes mellitus (according to ADA or WHO guidelines) with HbA1c not more than 12.0% at screening (Visit 1). Patients should be on diet, exercise, and/or pharmacological treatment for diabetes and should have a visual impairment due to focal or diffuse macular edema with center involvement in at least one eye, as demonstrated with color fundus photography, fluorescein angiography and OCT within 28 days of the baseline treatment. It is aimed to randomize a total of 86 patients in approximately 12 centers in Turkey. Since a 20% screening failure rate is expected, 104

	patients have to be screened.
Inclusion criteria	
 1. Written informed consent must be obtained before any assessment is performed. 2. Male or female patients >18 years of age who have signed an informed consent 3. Patients with Type 1 or Type 2 diabetes mellitus (according to ADA or WHO guidelines) with HbA1c not more than 12.0% at screening (Visit 1). Patients should be on diet, exercise, and/or pharmacological treatment for diabetes. 4. Patients with visual impairment due to focal or diffuse macular edema with center involvement in at least one eye, as demonstrated with color fundus photography, fluorescein angiography and OCT within 28 days of the baseline treatment. If both eyes are eligible, the one with the worse visual acuity, as assessed at Visit 1, will be selected for study treatment unless, based on medical reasons, the investigator deems the other eye the more appropriate candidate for study treatment. The study eye must fulfill the following criteria at Visit 1: 
 • BCVA score between 78 and 39 letters, inclusively, using ETDRS-like visual acuity testing charts at a testing distance of 4 meters (approximate Snellen equivalent of 20/32 to 20/160) • Decrease in vision is due to DME and not due to other causes, in the opinion of the investigator
Exclusion criteria	
Exclusion criteria
 
 1. Concomitant conditions in the study eye according to defined criteria such as infection, inflammation, uncontrolled glaucoma 2. Active proliferative diabetic retinopathy or evidence of vitreomacular traction in the study eye 3. Patients who are monocular or have a BCVA score in the non-study eye (fellow eye) \leq 24 letters (approximate Snellen equivalent of 20/320) at Visit 1 4. The history of vitrectomy in the study eye. 5. Concomitant systemic condition according to defined criteria, eg. history of stroke, uncontrolled diabetes, renal failure, unsatisfactory controlled hypertension 6. Use of other investigational drugs within 5 half-lives of enrollment, or within 30 days until the expected PD effect has returned to baseline, whichever is longer. 7. History of hypersensitivity to any of the study drugs or to drugs of similar chemical classes. 8. History of malignancy of any organ system (other than localized basal cell carcinoma of the skin), treated or untreated, within the past 5 years, regardless of whether there is evidence of local recurrence or metastases. 9. Pregnant or nursing (lactating) women, where pregnancy is defined as the state of a female after conception and until the termination of gestation, confirmed by a positive hCG laboratory test. 
Women of child-bearing potential, defined as all women physiologically capable of becoming pregnant, unless they are using effective methods of contraception during dosing of study treatment.

	
Women are considered post-menopausal and not of child bearing potential if they have had 12 months of natural (spontaneous) amenorrhea with an appropriate clinical profile (e.g. age appropriate, history of vasomotor symptoms) or have had surgical bilateral oophorectomy (with or without hysterectomy) or tubal ligation at least six weeks ago.
 
In the case of oophorectomy alone, only when the reproductive status of the woman has been confirmed by follow up hormone level assessment is she considered not of child bearing potential.

Investigational and reference therapy	The investigational drug in this study will be ranibizumab 0.5 mg. No additional treatment beyond investigational treatment is requested for this trial.
Efficacy assessments	
Mean change in Best-corrected visual acuity (BCVA) with ETDRS-like chart at a starting distance of 4 meters, at 12th month from baselineMean change in CRT (μm) by Optical coherence tomography at 12th month from baselineMean no. of injections over a 12-month treatment periodMean no. of visits over a 12-month treatment periodProportion of patients who gained ≥0, ≥5, ≥10 and ≥15 letters in BCVA at 12th monthMean change in VFQ25 scores at 12th month from baseline
Safety assessments	
Incidence of adverse events (AEs) and serious AEs (SAEs), by ophthalmic examinations and IOP measurements, and by changes in vital signs and laboratory parameters over the 12-month assessment period.
Other assessments	There is no other planned analysis to be performed for this study.
Data analysis	A sample size of 86 (43 for each treatment arm) can achieve 90% power to detect non-inferiority limit of 5 letter between treatment arm when significance level of the test is 0.025 and the mean (standard deviation) letter change of labeled regime arm will be around 7 (7). To eliminate the effects of incomplete data which are expected in 1 year follow-up period, a priori 20% of drop-out rate is accepted; therefore at least 104 patients (52 for each treatment arm) will be included to the study.
Key words	Optic Coherence Tomography, Diabetic Macular Edema, Ranibizumab, Tolerability, Safety, Wait and Extend

1 Introduction

1.1 Background

Diabetes mellitus (DM) is the most common endocrine disease in developed countries, with prevalence estimates ranging between 2 to 5% of the world's population. Diabetic retinopathy (DR) and diabetic macular edema (DME) are common microvascular complications in patients with diabetes and may have a sudden and debilitating impact on visual acuity (VA), eventually leading to blindness. DME is a frequent manifestation of DR [Riordan-Eva, 2004] and is the major cause of visual loss in patients with DR.

If left untreated, >50% of patients lose >2 lines of visual acuity (VA) within 2 years. DME mostly affects the working-age population, imposing a significant burden both on society and on individual patients - a burden that is expected to increase with the rising prevalence of diabetes [Bandello, 2012]

Diabetic macular edema (DME) can occur at any stage of non-proliferative and proliferative diabetic retinopathy. It is characterized by a swelling of the macular area that normally accounts for high-resolution visual acuity (VA), and DME therefore leads to visual deterioration. Clinically significant DME (CSME) is defined as retinal thickening with or without hard exudates within one diameter of the macular center and results in visual impairment when the foveola is involved. This is referred to as CSME with center involvement (CSME-CI) [Lang, 2012].

One important aspect of the pathophysiology of DME is that cytokine signaling and expression are deregulated in patients with diabetic retinopathy. The permeability of retinal endothelial cells (REC) is controlled by VEGF and regulated by its binding to the VEGF receptor 2. DME results from a breakdown of the blood-retinal barrier and leads to retinal thickening caused by an accumulation of fluid and molecules in the retina. The leakage can arise from microaneurysms or capillaries. The primary endogenous mediator of DME is VEGF, a glycoprotein that is secreted by REC, pericytes and pigment epithelial cells. REC dysfunction seems to be an important step in the development of DME. Hyperglycemia and hypoxia-induced VEGF release are important confounding factors [Lang, 2012].

For the last decades, laser was the gold standard for the treatment of patients with CSME. This treatment, however, is destructive and it rather prevents further visual deterioration than improves vision. Therefore, new treatment modalities were developed to overcome the unmet medical need to restore vision [Lang, 2012].

Ranibizumab (Lucentis) is a recombinant humanized IgG1 κ isotype monoclonal antibody fragment (Fab) that selectively binds VEGF. Ranibizumab (intravitreal injections of 0.5 mg) is approved for the treatment of neovascular age-related macular degeneration (AMD), the treatment of visual impairment due to diabetic macular edema (DME) and the treatment of

visual impairment due to macular edema secondary to retinal vein occlusion (branch RVO or central RVO) in a number of countries worldwide [Product information].

Five trials, ie, two DRCR.net trials, RESTORE, RISE, and RIDE, have provided level I evidence supporting use of ranibizumab for the treatment of DME, and two additional trials have provided level II evidence. These trials demonstrate that ranibizumab therapy for DME is safe and effective for two years [Stewart, 2013] The approval of ranibizumab for patients with visual impairment due to DME with center involvement has improved the visual prognosis and offers therapy for an up to now unmet medical need [Lang, 2012].

The recommended dose for Lucentis is 0.5 mg given monthly as a single intravitreal injection.

Treatment is continued until maximum visual acuity is achieved i.e the patient's visual acuity is stable for three consecutive monthly assessments performed while on ranibizumab treatment. Thereafter patients should be monitored monthly for visual acuity. Treatment is resumed when monitoring indicates loss of visual acuity due to DME. Monthly injections should then be administered until stable visual acuity is reached again for three consecutive monthly assessments. The interval between two doses should not be shorter than 1 month. However, there is a need to explore a more clinical feasible treatment regime to provide satisfactory treatment effect with a lower number of visits and injections [Product information]

A "wait and extend" regimen has been demonstrated efficient for treatment of wAMD in SALUTE study as mentioned above and found to be safe and tolerable [ASRS 2013]. The rationale of this pilot study is to show that similar approach is applicable in treatment of DME.

According to the SALUTE study performed in Turkey with 104 screened patients, Ranibizumab usage with Wait & Extend or Treat & Observe approach provided improvements in terms of best corrected visual acuity and central retinal thickness. and no significant differences between treatment approaches were found. In per protocol population; visit count in Wait & Extend group is significantly lower than Treat & Observe group. In conclusion, using ranibizumab in patients with choroidal neovascularisation due to AMD with Wait & Extend regimen seems to be as efficient, safe and tolerable as Treat & Observe regimen with less number of visits [ASRS 2013].

The rationale of this pilot study is to show that similar approach is applicable in treatment of DME.

1.2 Purpose

The purpose of this study is to demonstrate the non-inferiority of "wait and extend" regimen of ranibizumab to labeled posology in Turkish patients with visual impairment due to diabetic macular edema with respect to the mean change in BCVA at 12th month from baseline..

2 Study objectives

2.1 Primary and key secondary objectives

The primary objective of this study is to demonstrate the non-inferiority of “wait and extend” regimen of ranibizumab to labeled posology in Turkish patients with visual impairment due to diabetic macular edema with respect to the mean change in BCVA at 12th month from baseline.

2.2 Secondary objectives

- to compare mean change in CRT at 12th month from baseline between two groups with OCT
- to assess the number of injections needed over a 12-month treatment period with a “wait and extend” dosing regimen
- to assess the number of visits needed over a 12-month treatment period with a “wait and extend” dosing regimen
- to evaluate the number of patients with improvement in BCVA from baseline
- to evaluate the number of patients with improvement of 5 or more letters from baseline
- to evaluate the number of patients with improvement of 10 or more letters from baseline
- to evaluate the number of patients with improvement of 15 or more letters from baseline
- to evaluate the safety of intravitreal injections of Lucentis (ranibizumab) in patients with DME
- to describe the change in Patient reported functional ability of Lucentis-treated patients.

2.3 Exploratory objectives

Not Applicable

3 Investigational plan

3.1 Study design

This is a randomized controlled, multicenter, 12 month study of Lucentis (ranibizumab) that the consenting patients will participate in a screening period and will be evaluated for their eligibility to enroll the study. After the screening period and the eligibility assessment of the patient, only one eye will be selected / treated as the study eye. After eligibility confirmation at baseline, patients will be randomized into one of the treatment arms as below:

- Arm 1 - Labeled regime arm: Treatment will be given monthly and will be continued until maximum visual acuity is achieved (the patient's visual acuity is stable for three consecutive monthly assessments performed while on ranibizumab treatment). Thereafter patients should be monitored monthly for visual acuity.
- Retreatment criteria:
 - According to this protocol VA stability means BCVA \geq 84 letters (approximate Snellen equivalent of 20/20) or OCT <300 microns in the last 2 consecutive visits or no improvement can be achieved according to the investigators evaluation regarding VA and OCT measures in the last 2 visits . Stable patients do not require reinjection and should be evaluated in the next visit for reinjection.
 - If VA decreases \geq 5 letters compared to previous visit and OCT is >300 microns, patients will be retreated.
 - If VA decreases \geq 5 letters compared to the previous visit or CRT increases >50 microns compared to the previous visit, patients will be retreated.
 - After 3 monthly injections of the investigational drug laser photocoagulation can be administered if VA worsens \geq 10 letters and/or CRT increases >100 microns.
- The interval between two doses should not be shorter than 1 month.
- Arm 2 - Wait and Extend regime arm: Lucentis (ranibizumab) 0.5 mg will be injected subsequently at baseline, month 1 and 2. After the three initial loading doses, patients will be called for the control visits 1 month later. If the visual acuity has reached a stable level and there is no sign of edema on OCT, patients will not receive intravitreal injection and will be called to come back 6 weeks later. The interval is increased by 2 weeks until a maximum of 8 weeks as long as the patient presents as stable regarding visual acuity, central retinal thickness and clinical findings. If there is a negative change, the interval is shortened back to 4 weeks.

Retreatment criteria:

- According to this protocol VA stability means BCVA \geq 84 letters (approximate Snellen equivalent of 20/20) or OCT <300 microns in the last 2 consecutive visits or no improvement can be achieved according to the investigators evaluation regarding VA and OCT measures in the last 2 visits . Stable patients do not require reinjection and should be evaluated in the next visit for reinjection.
- If VA decreases \geq 5 letters compared to previous visit and OCT is >300 microns, patients will be retreated.
- If VA decreases \geq 5 letters compared to the previous visit or CRT increases >50 microns compared to the previous visit, patients will be retreated.
- After 3 monthly injections of the investigational drug laser photocoagulation can be administered if VA worsens \geq 10 letters and/or CRT increases >100 microns.

Figure 3-1 Study design

Study Design For Labelled Regime Arm

Phase	Screening		Main Treatment			
Visit	1	2	3	4	5	6 -14
Month	0		1	2	3	4 – 12
Day	-7 to -1	B	30	60	90	120 – 360

Study Design For Wait and Extend Arm

Phase	Screening		Main Treatment			
Visit	1	2	3	4	5	Visit number may vary according to the response of the patient
Month	0		1	2	3	4 – 12
Day	-7 to -1	B	30	60	90	120 – 360

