5.2 Treatment arms

Patients will be assigned to one of the following “2” treatment arms randomly

A study-specific randomization scheme will be prepared by the CRO to follow up the randomization.

- Arm 1 - Labeled regime arm: Treatment will be given monthly and continued until maximum visual acuity is achieved (the patient’s visual acuity is stable for three consecutive monthly assessments performed while on ranibizumab treatment). Thereafter patients should be monitored monthly for visual acuity.

Treatment is resumed when monitoring indicates loss of visual acuity due to DME. Monthly injections should then be administered until stable visual acuity is reached again for three consecutive monthly assessments (implying a minimum of two injections). The interval between two doses should not be shorter than 1 month.

- Arm 2 - Wait and Extend regime arm: Lucentis (ranibizumab) 0.5 mg will be injected subsequently at baseline, month 1 and 2. After the three initial loading doses, patients will be called for control 1 month later. If the visual acuity has reached a stable level and there is no sign of edema on OCT, patients will not receive intravitreal injection and will be called to come back 6 weeks later. The interval is increased by 2 weeks until a maximum of 8 weeks as long as the patient presents as stable regarding visual acuity, central retinal thickness and clinical findings. If there is a negative change, the interval is shortened back to 4 weeks.

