4 STUDY DESIGN

Study Design for the Prescribing Information Regimen Arm

Phase	Screening		Main Treatment			
Visit	1	2	3	4	5	6 -14
Month	0		1	2	3	4 – 12
Day	–7 to –1	B	30	60	90	120 – 360

Study Design for the Wait and Extend Regimen Arm

Phase	Screening		Main Treatment			
Visit	1	2	3	4	5	Number of visits may vary by patient response
Month	0		1	2	3	4 – 12
Day	–7 to –1	B	30	60	90	120 – 360

This is a randomized, controlled, multicenter, 12-month study concerning Lucentis (ranibizumab). Patients who provide consents will enter a screening period and their eligibility for enrollment will be evaluated. Following the screening period and evaluation of patient eligibility, only one eye will be selected / treated as the study eye. Once eligibility is confirmed, patients will be randomized to one of the following treatment arms:

Arm 1: Prescribing information regimen arm: Treatment will be given monthly and maintained until maximum visual acuity is achieved (patient's visual acuity remaining stable for three consecutive monthly assessments performed during ranibizumab treatment). Thereafter, patients will be followed-up monthly for visual acuity.

Treatment will be reinitiated in case a loss in visual acuity due to DME is determined during follow-up. Thereafter, monthly injections are to be performed until stable visual acuity is achieved for three consecutive monthly assessments (refers to at least two injections). The period between two doses should not be shorter than 1 month.

Arm 2: Wait and extend regimen arm: Lucentis (ranibizumab) 0.5 mg will be injected at baseline, and at months 1 and 2. Following the three loading doses at baseline, patients will be invited for a follow-up visit one month later. Once visual acuity becomes stable and OCT demonstrates no evidence of edema, patients will no longer be given intravitreal injections and they will be invited to return 6 weeks later. The interval will be extended by 2 weeks for a maximum of 8 weeks for as long as the patient exhibits stable visual acuity, central retinal thickness and clinical findings. In the event of a negative change, the interval will be reduced back to 4 weeks.

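### Arm 1 is described both as the acuity-based label and by Section 3.1 bullets that add OCT rules; in both arms those bullets overlap with no stated precedence.

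*Protocol*

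**What the plan says.** **Acuity-based description of Arm 1.** The Arm 1 paragraph in Protocol Section 3.1 continues monthly treatment until "visual acuity is stable for three consecutive monthly assessments performed while on ranibizumab treatment". The synopsis, Section 5.2 and SAP 4 set the same stopping condition. On resumption the synopsis says "Treatment will be resumed when monitoring indicates loss of visual acuity due to DME", and SAP 4 says "Treatment will be reinitiated in case a loss in visual acuity due to DME is determined during follow-up". Section 5.2 continues resumed monthly injections "until stable visual acuity is reached again for three consecutive monthly assessments (implying a minimum of two injections"; the synopsis and SAP 4 give the same minimum of two. Section 1.1 summarises the label in these acuity terms, without the two-injection remark.

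**Bullets in Section 3.1, identical for the two arms.** Stability is defined as BCVA of at least 84 letters, or "OCT <300 microns in the last 2 consecutive visits or no improvement can be achieved according to the investigators evaluation". The consequence is "Stable patients do not require reinjection and should be evaluated in the next visit for reinjection". Two retreatment bullets follow. The first requires a fall of at least 5 letters together with OCT above 300 microns. The second requires a fall of at least 5 letters "compared to the previous visit or CRT increases >50 microns compared to the previous visit, patients will be retreated".

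**Claim about the comparator.** Section 3.3 states that the Arm 1 regimen agrees with product labeling. The primary objective (Protocol 2.1, SAP 3.1) is non-inferiority to the labeled posology, and the titles in the synopsis and SAP 2 name the same comparator.

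**The concern.** In a non-inferiority trial the meaning of the conclusion depends on what the comparator was. Two descriptions of Arm 1 are in force, and the one with operational detail adds OCT-based rules that the other lacks. A site working from the Section 3.1 bullets would deliver something other than the regimen that the title and objective name. The number of injections, a secondary variable (Protocol 9.5.1), also depends on which rule is followed.

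Separately, a site facing a visit that satisfies both the stability definition and a retreatment trigger has no written instruction on which governs. The trial is open-label, in about 12 centers, without an adjudication committee, so nothing in the plan would make sites resolve this alike.

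**Working it through.** No figure in the plan bears on this point, and the sample size of 86 does not depend on it. The check sets the passages side by side and then applies the bullets as logical conditions.

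**Step 1. Arm 1, side by side**

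| Element | Synopsis, 5.2, SAP 4 | Label as summarised in 1.1 | Bullets in 3.1 |
|---|---|---|---|
| Stable | Acuity, three monthly assessments | Acuity, three monthly assessments | BCVA at least 84; or OCT <300 over 2 visits; or investigator sees no improvement over 2 visits |
| Resume | Acuity loss due to DME | Acuity loss due to DME | Loss of 5 or more letters, or CRT rise >50 without acuity loss |
| Minimum injections per resumed episode | Two | No number | None stated |

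The tension is also inside Section 3.1: its Arm 1 paragraph keeps three assessments, while its bullets use two visits.

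**Step 2. The bullets as conditions.** Let V0, V1 be BCVA and C0, C1 be CRT at the previous and current visit. I assume that the OCT value in microns is CRT.

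- Stable by OCT: C0 < 300 and C1 < 300. Stable by BCVA: V1 ≥ 84. The investigator-judgement limb has no numeric bound and is left out.
- Trigger A: V0 − V1 ≥ 5 and C1 > 300.
- Trigger B: V0 − V1 ≥ 5 or C1 − C0 > 50.

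A's first condition is by itself enough for B, so A never fires without B. The 300-micron condition in A therefore has no effect.

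**Step 3. Illustrative visits (constructed, not data)**

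| Case | BCVA | CRT | Stable by | A | B |
|---|---|---|---|---|---|
| 1 | 70 to 70 | 320 to 380 | neither numeric limb | no | yes, 380 − 320 = 60 |
| 2 | 60 to 66 | 290 to 280 | OCT | no | no |
| 3 | 70 to 64 | 270 to 280 | OCT | no, 280 is below 300 | yes, 70 − 64 = 6 |
| 4 | 70 to 70 | 230 to 285 | OCT | no | yes, 285 − 230 = 55 |
| 5 | 84 to 84 | 310 to 365 | BCVA | no | yes, 365 − 310 = 55 |
| 6 (after 3) | 64 to 66 | 280 to 275 | OCT | no | no |

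- Case 1 is retreated under the bullets. With no acuity loss, the acuity-based text gives no ground for resuming.
- Case 2 is stable under the bullets although acuity has just risen by 6 letters.
- Cases 3, 4 and 5 are stable and are also to be retreated.
- Case 6 shows that, with the bullets read alone, an episode can end after one injection.

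**Step 4. Where the overlap can occur, in whole numbers**

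- OCT limb with a CRT rise: C1 ≤ 299 and C1 − C0 ≥ 51 give C0 ≤ 299 − 51 = 248. Any loss of 5 or more letters also overlaps with this limb.
- BCVA limb with a letter loss: V1 ≥ 84 and V0 − V1 ≥ 5 give V0 ≥ 89. With a CRT rise above 50 there is no bound on C0.
- Entry BCVA is at most 78 (Section 4.1), so 84 needs a gain of at least 6 letters and 89 at least 11. The planned mean gain is about 7 (Section 9.7). The OCT limb is the more accessible route, since the inclusion criteria set no minimum CRT.

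**Step 5. Minor mismatches.** Rescue laser is allowed at a loss of 10 or more letters in Section 3.1 but more than 10 in Section 5.5.6. These differ only at exactly 10 letters without a CRT rise above 100 microns. Footnote d of the visit schedule ties later injections to lesion activity under an outside body's criteria, which are not linked to Section 3.1.

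**The case against.** **The bullets only make the label workable.** The label summary defines neither stable acuity nor loss due to DME, so a protocol has to, and OCT can help attribute a loss to DME. That is fair for numeric thresholds. It does not cover retreatment with no acuity loss (case 1), nor stability on OCT alone.

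**The bullets sit under a paragraph that keeps the three-assessment rule.** This stands. Case 2, and the one-injection episode in case 6, follow only if the bullets are read alone. A site applying Sections 3.1 and 5.2 together could still give the second injection.

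**The overlap has an ordinary resolution.** Saying that stable patients need no injection does not forbid one, whereas the trigger wording is mandatory. The Arm 2 text points the same way: extension applies while the patient is "stable regarding visual acuity, central retinal thickness and clinical findings. If there is a negative change, the interval is shortened back to 4 weeks". So a reader might infer a flat contradiction, but the documents support only an ambiguity. Retreatment probably prevails, yet no sentence says so, and the stability bullet defers evaluation for reinjection to the next visit.

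**Stronger inferences that the documents do not support**

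- That the arms are affected differently: the bullets are the same in both.
- That visits without an injection would be counted as missed doses (Section 5.5.9) or as non-compliance (Section 6.3): no passage counts them so.
- That Arm 1 departs from the label itself: the label is not in the documents, only the summary in Section 1.1.

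**Conclusion.** The point holds as an inconsistency in how the comparator is defined. Under the Section 3.1 bullets, Arm 1 includes a CRT-only retreatment trigger and an OCT-only route to stability. Neither appears in the synopsis, Section 5.2, SAP 4 or the label summary. Section 3.1 also omits the two-injection minimum. If sites follow the bullets, the trial would show non-inferiority to a protocol-defined regimen and could not, as worded, support the stated conclusion about labeled posology.

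The unwritten precedence between stability and retreatment, in both arms, is secondary. The redundant trigger, the rescue threshold and footnote d are minor.

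The size cannot be given in letters or patients. The documents do not say how often such visits occur or which text sites followed, and no effect on BCVA can be derived. The textual mismatch is certain; its consequences are not. The cases assume that OCT microns means CRT and leave out the investigator-judgement limb. It should be fixed, because it decides what the trial can claim.

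**What to change.** The sponsor should reconcile the synopsis, Section 3.1 (both arms), Section 5.2, Section 5.5.6, footnote d of the visit schedule and SAP 4 into one rule set per arm. Each set needs a single definition of stability and a written order of precedence where stability and retreatment conditions are both met. The clinical content is for the sponsor to choose; this review takes no view on which rule is right.

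The synopsis title, Sections 1.1, 2.1 and 3.3, and SAP 2 and 3.1 should then be aligned with it, so that the comparator named in the title, objective and conclusion is the regimen Arm 1 actually receives.

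The cost is a written amendment with the approvals in Section 11.1, a matching SAP edit and site retraining. No new assessments are needed, since acuity and OCT are already measured at the control visits. If patients are already enrolled, which the documents do not show, the date of the change should be recorded and patients treated before and after it reported. That discloses a mix of rules within each arm but does not remove it.
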